# **7.3.2** Dietary Supplements

Participants who are currently consuming the following supplements will not be allowed to participate unless willing to undergo the specified washout period prior to their baseline visit and agree not to take the supplements during the study. Other OTC supplements and food/drinks will require a case-by-case assessment by the QI based on dose and/or frequency of use to determine adequate washout. All washouts to be ensured to happen prior to enrollment.

- 1. Senegalia catechu (2-day washout)
- 2. Scutellaria baicalensis (7-day washout)
- 3. Aloe vera
- 4. Rosemary extract
- 5. Echinacea (2-day washout)
- 6. Astragalus (2-day washout)
- 7. Ginseng (25-day washout)
- 8. Turmeric (3-day washout)
- 9. Medicinal mushroom
- 10. Probiotics (30-day washout)
- 11. Beta-glucan (30-day washout)

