## Removal by Qualified Investigator

Participant discontinuation should be considered at the discretion of the Qualified Investigator. The circumstances of any discontinuation must be documented in detail in the participant file and final report. If possible, the evaluations planned for the end of study will be carried out at the time when the participant is withdrawn from the study.

Criteria for removal of participants from the study includes:

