#### Clinical reasons

A participant may be withdrawn from the study if, in the opinion of the Qualified Investigator, it is not in the participant's best interest to continue. Any participant who experiences a serious adverse event (SAE) may be withdrawn from the study at the discretion of the Qualified Investigator. A participant will also be withdrawn due to adverse events causing clinically significant illness or the need for prohibited medication(s) during the study. Any female participant who becomes pregnant during the study will be withdrawn and followed up with until giving birth.

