## Protocol violation

Any participant found to have entered this study in violation of the protocol will be discontinued from the study at the discretion of the Qualified Investigator. This will include any participant found to have been inappropriately enrolled (did not meet eligibility criteria). Participant non-compliance includes failure to show up for study visits, failure to take the investigational product as directed, or refusal to undergo study visit procedures. Participants who are found to be taking prohibited medications or supplements without the knowledge of the Qualified Investigator will also be withdrawn. Any major protocol deviations (i.e. those that increase the risk to participants and/or compromise the integrity of the study or its results) will result in participant discontinuation.

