#### Participant Replacement

For all early withdrawals, a participant leaving the study prematurely or in the event of participant removal will be assessed at the time of dropout based on the rates of attrition at that time. It is understood by all concerned that an excessive rate of withdrawals can render the study un-interpretable, thus unnecessary withdrawal of participants should be avoided.

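### Section 7.5 ends follow-up as well as product use on three grounds, so a participant removed at Day 28 before vaccination has no observed post-vaccine primary value

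*Protocol*

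**What the plan says.** The list in Protocol 7.5 opens with "Criteria for removal of participants from the study includes", so it concerns leaving the study, not only stopping the capsules. Three grounds are worded as something that will happen:

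- **Barred therapy unknown to the investigator:** "Participants who are found to be taking prohibited medications or supplements without the knowledge of the Qualified Investigator will also be withdrawn".
- **Adverse events:** a participant "will also be withdrawn due to adverse events causing clinically significant illness or the need for prohibited medication(s) during the study".
- **Major deviations:** these are defined as deviations that raise risk to participants and/or "compromise the integrity of the study or its results) will result in participant discontinuation".

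The section also contains softer wording. The paragraph on removal by the Qualified Investigator begins by leaving discontinuation to that investigator's discretion, and the paragraph on replacement says that "unnecessary withdrawal of participants should be avoided". Poor adherence, "failure to take the investigational product as directed", is listed as non-compliance with no mandatory consequence. Section 9.9.7 responds to compliance outside 80% to 120% with counselling.

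Where possible, "the evaluations planned for the end of study will be carried out at the time when the participant is withdrawn". Section 10.2.2 has a route that stops product and keeps the visits. It covers only participant-initiated withdrawal and clinically significant unexplained laboratory values, and it labels those participants a safety arm.

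Under 7.3.2, users of listed supplements must wash out and "agree not to take the supplements during the study".

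**The concern.** The trial uses influenza vaccination as the immune challenge. Vaccine is given at Day 28, and the primary outcome is measured at baseline, Day 28 and Day 56, so Day 56 alone shows the response to vaccine. A rule that ends follow-up because of something that happened after randomization removes that value for the people concerned.

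Such losses need not be random. Adverse events can depend on the product. A participant who feels unwell may plausibly start an immune supplement such as echinacea, which is on the barred list. The chance of losing the Day 56 value could then be related to arm and to immune status. A mixed model corrects only for what the baseline and Day 28 values predict.

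Removal is also not needed to protect a clean comparison. Section 11.2 already excludes from the Per Protocol (PP) set anyone with a deviation that affects the primary outcomes.

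**Working it through.** **1. Sequence at Day 28 (9.6).** Diaries are reviewed at item 1, concomitant therapies and adverse events at item 3, blood is drawn at item 5 and vaccine is given at item 8. Someone removed at item 1 or 3 leaves before vaccination. Bringing the end-of-study evaluations forward gives a primary blood value, but a pre-vaccine one. With Day 28 data the participant remains in the ITT set of 11.2, without an observed Day 56 value. Someone removed after vaccination can still give a post-vaccine sample, though an early one.

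**2. The plan's own figure (11.1).** The plan has 25 per arm with a 20% loss allowance. 25 × (1 − 0.20) = 20 evaluable, and 20 / 0.80 = 25, so the allowance is consistent. Section 11.1 gives detectable differences but no SDs, so the sample size itself cannot be reproduced. With 20 per arm, one-sided 5% (11.3) and 80% power, the pairwise detectable difference is (1.645 + 0.842) × √(2/20) = 0.786 SD.

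**3. Possible bias without carry-forward.** Let k be the excess of removals in one arm. Let D be how far the unseen Day 56 values depart, in SD units, from what baseline and Day 28 predict. Neither is in the protocol. I assume k = 1 to 5 (5 of 25 uses the whole 20% allowance) and D = 0 to 1.

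Shift = (k/25) × D. Standard error = √(1/25 + 1/(25 − k)). True one-sided error = 1 − Φ(1.645 ∓ shift/SE), with minus if the shift favours product and plus if it goes against.

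| k | D | Shift (SD) | SE | Error if favouring product | Error if against |
|---|---|---|---|---|---|
| 1 | 0.25 | 0.01 | 0.286 | 5.4% | 4.6% |
| 3 | 0.5 | 0.06 | 0.292 | 7.5% | 3.2% |
| 5 | 1 | 0.20 | 0.300 | 16.4% | 1.0% |

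With D = 0 there is no bias. The range of 0 to 0.20 SD is 0% to 25% of 0.786 SD.

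**4. If carry-forward is used.** Section 11.3 names LOCF or multiple imputation. Under LOCF, a pre-vaccine value would stand as the Day 56 value, and each such participant would take 1/25 of the mean vaccine-period change off the arm mean.

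**5. Power if these participants are kept.** Assume five per arm. Let f be the share of the product effect present in those kept on product, and g the share acquired by those kept on placebo. The second term is needed because *Senegalia catechu*, *Scutellaria baicalensis*, aloe vera and rosemary extract are both barred supplements (7.3.2) and product ingredients (8.3, 8.4).

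Contrast = 0.786 × [1 − (5/25)(1 − f) − (5/25)g]. Power = Φ(contrast/√(2/25) − 1.645), with √(2/25) = 0.283.

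| f | g | Contrast (SD) | Power |
|---|---|---|---|
| 1 | 0 | 0.786 | 87.2% |
| 0.5 | 0 | 0.708 | 80.4% |
| 0 | 0 | 0.629 | 71.9% |
| 0.5 | 0.5 | 0.629 | 71.9% |
| 0 | 1 | 0.472 | 50.9% |

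If the five per arm are removed, power is 80.0% by construction.

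**The case against.** The strongest reply is that the rule is narrower and softer than it looks, and several parts of that reply stand.

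- **Discretion.** A reader might infer an absolute mandate. The opening sentence on discretion and the advice against unnecessary withdrawal do not support that; the section mixes discretion with firm wording. The three sentences still carry no qualifier of their own, and none of them offers stopping product alone.
- **Scope.** A reader might infer that every user of a barred product must leave, or that low compliers must. The first sentence covers only use unknown to the investigator, and 9.9.7 and the 80% PP criterion imply that low compliers can stay. Some major deviations concern participant risk, where removal can be right.
- **Mechanism.** A reader might infer that a cold, or a cold remedy, triggers removal. Section 10.1.1 keeps respiratory symptoms listed on the WURSS-24 out of the adverse events, and ordinary cold medicines are not named in 7.3.1 or 7.3.2. What remains is undisclosed use of a listed product and genuine adverse-event withdrawals.
- **Contamination.** Keeping a placebo participant who takes a product ingredient dilutes the contrast, so excluding such use is a defensible choice. The second term in step 5 allows for this.

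The reply does not supply the missing value. Section 10.2.2 does not reach these grounds, the early evaluation at Day 28 is pre-vaccine, and the 20% allowance covers lost numbers but not bias. The choice of imputation can be left to an analysis plan, but no imputation recovers blood that was never drawn.

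**Conclusion.** The point holds in limited form. On three grounds 7.5 directs withdrawal from the study with no product-only alternative, and a participant removed at Day 28 before vaccination has no observed post-vaccine primary value.

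The size rests on assumed k and D. The middle case is a shift of 0.06 SD and a one-sided error of 7.5% or 3.2%, depending on direction. The 16.4% case needs a five-participant excess in one arm together with a full 1 SD of unexplained departure. The protocol gives no frequency, and the direction cannot be known in advance, so it does not support a claim that the results would be biased towards the products. The effect is probably modest.

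The gain from changing the rule is more complete ITT data with less scope for bias, not assured power. I would offer it as an optional improvement.

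**What to change.** Add to 7.5 that the three grounds may end product use but not follow-up. Day 28 vaccination (unless contraindicated or excluded under 9.5) and the Day 56 assessments then continue, unless the participant declines or safety requires removal. State that observed Day 56 values enter the ITT analysis, not only a safety arm, and that deviations serve only to define the PP set. Name the adverse-event ground explicitly, since an adverse event is not a deviation and the product-dependence argument rests on it. Section 9.9.7 needs no change.

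The cost is a wording amendment; the Day 56 visit is already scheduled. The drawback is the dilution shown in step 5, with the PP analysis remaining as the undiluted comparison. The change does not recover data from participants who miss visits or refuse procedures.

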#### Participant Replacement

For all early withdrawals, a participant leaving the study prematurely or in the event of participant removal will be assessed at the time of dropout based on the rates of attrition at that time. It is understood by all concerned that an excessive rate of withdrawals can render the study un-interpretable, thus unnecessary withdrawal of participants should be avoided.

#### 8 INVESTIGATIONAL PRODUCT

## 8.1 Manufacturing and Storage

The investigational product will be provided to KGK Science Inc. by the Sponsor. The investigational product will be carefully stored at the study site in a lockable, limited access area, accessible only to study team personnel in compliance with pertinent regulations. Only authorized persons will have access to the investigational product. The products will be stored at room temperature and will not be exposed to direct sunlight or heat. The investigational products will be kept in a locked investigational product storage room at KGK Science Inc. on receipt. An accountability log will be kept for the investigational products.

All unused investigational product will be returned to the study Sponsor by KGK Science Inc. (at the Sponsor's expense) or destroyed on receipt of written confirmation from the Sponsor at study closeout (within one month of last participant visit).

Manufactured by:

Rose City Nutritionals, LLC

#### 8.2 Labelling and Coding

The investigational product will be labeled according to the requirements of ICH-GCP guidelines and applicable local regulatory guidelines. Investigational product will be randomized and coded by an unblinded person at KGK who is not involved in data collection or analysis.

#### 8.3 **UP360** (per 500 mg capsule)

Dietary Ingredient	Quantity
Aloe vera gel powder	150 mg
Rosemary extract	50 mg
Poria cocos extract	100 mg

Non-medical ingredients: Polydextrose, Microcrystalline cellulose (MCC), and magnesium stearate

## 8.4 **UP446** (per 250 mg capsule)

Dietary Ingredient	Quantity
Acacia catechu (Senegalia catechu)	50 mg
Scutellaria baicalensis	200 mg

Non-medical ingredients: Maltodextrin, MCC, and magnesium stearate

# 8.5 Placebo

Ingredients: MCC and magnesium stearate

### 8.6 Directions for Investigational Products and Placebo

Participants will be instructed to take two capsules per day, one in the morning and one in the evening around mealtimes with food and 4-6 ounces of water for 56 days, beginning on Day 0. Clinic staff will instruct participants to save all unused and open packages and return them to KGK Science Inc. for a determination of compliance. If a dose is missed, participants are instructed to take the dose as soon as possible. Participants will be advised not to exceed 4 capsules daily.

#### 8.7 Rescue Medication

Rescue medication is not applicable for this study.

#### 8.8 Quadrivalent Influenza Vaccine

FLUCELVAX® QUAD, Drug Identification Number (DIN) 02494248, is a QIV designed for immunization of adults and children above the age of 9 for the prevention of influenza from subtypes A and B.

Strains	Quantity/Dose
Haemagglutinin A/Hawaii/70/2019 (H1N1) pdm09-like virus (A/Nebraska/14/2019)	15 μg
Haemagglutinin A/Hong Kong/45/2019 (H3N2)-like virus (A/Delaware/39/2019)	15 μg
Haemagglutinin B/Washington/02/2019-like virus (B/Darwin/7/2019)	15 μg
Haemagglutinin B/Phuket/3073/2013-like virus (B/Singapore/INFTT-16-0610/2016)	15 μg

Non-medical ingredients: Disodium phosphate dihydrate, Magnesium chloride hexahydrate, Potassium chloride, Potassium dihydrogen phosphate, Sodium chloride, Water for injections, beta-propiolactone, cetyltrimethylammonium bromide, polysorbate 80

# 8.9 Directions for Quadrivalent Influenza Vaccine

The QIV will be kept under proper storage with refrigeration kept between 2 to 8°C. The QIV will be administered via intramuscular injection using proper techniques and sanitation, preferably in the deltoid muscle of the upper arm, on Day 28.

#### 8.10 Randomization

A randomization schedule will be created and provided to the Qualified Investigator indicating the order of randomization. Each participant will be assigned a randomization code according to the order of the randomization list generated using www.randomization.com. Enrolled participants will be randomized to the different study arms at day 0. One gender will not exceed 65%.

#### 8.11 **Blinding and Allocation Concealment**

Concealment of the allocation of study arms will be employed through the use of opaque sealed envelopes, each labeled with a randomization number. Each envelope will contain information regarding the study arm associated with each randomization number. These envelopes will be readily available for the Qualified Investigator to open in the event that it becomes necessary to know which product a participant is taking for the sake of the participant health care.

Unblinding should not occur except in the case of emergency situations. In the event that a serious adverse event occurs, for which the identity of the investigational product administered is necessary to manage the participant's condition, the study arm assigned to the participant will be unblinded and the investigational product identified. The Sponsor must be notified of any unblinding within 24 hours. Details of participants who are unblinded during the study will be included in the Final Report.

#### 9 STUDY ASSESSMENTS

## 9.1 Screening (Day -45 to Day -4)\*

\* At the discretion of the Qualified Investigator, any participants falling outside of the screening window (Day -45 to Day -4) due to scheduling issues will be asked to repeat eligibility/screening procedures prior to randomization at baseline.

An informed consent form will be given to the potential volunteer. They will be required to read the information and will be given the opportunity to seek more information if needed or provided with the option of keeping a copy of the consent form to review prior to making their decision. If agreeable, the volunteer will sign the consent form and receive a duplicate of the signed copy. Once consent has been obtained, the screening visit will proceed. Each volunteer will be sequentially assigned a screening number to be entered in the screening and enrollment log.

#### Screening assessments include:

- 1. Review medical history, concomitant therapies and current health status
- 2. Assess inclusion and exclusion criteria
- 3. Collect information regarding demographics, alcohol, cannabis, and tobacco habits, diet, sleep, and exercise habits, allergy history, upper respiratory tract infection history, and flu vaccine history
- 4. Collect blood samples for the analysis of CBC, electrolytes (Na, K, Cl), HbA1c, glucose, eGFR, creatinine, AST, ALT, ALP, and total bilirubin
- 5. Dispense modified WURSS-24 Questionnaires and instruct participants on completion. The WURSS-24 Questionnaire is to be completed for the 3 days prior to baseline to establish a preintervention level of upper respiratory tract infection symptoms for each participant and ensure participants are not sick at the time of baseline (Section 9.9.3)
- 6. Dispense study diaries and instruct participants on completion to record the following during the run-in period:
  - a. AEs
  - b. Concomitant medication
  - c. Hours of sleep
  - d. Alcohol intake
  - e. Tobacco use
  - f. Cannabis use
  - g. Hours and description of exercise
  - h. Self-reported COVID-19 diagnosis based on positive COVID-19 test
- 7. Record any pre-emergent AEs

The next appointment will be scheduled within 45 days for potentially eligible participants for their baseline.

Participants will be reminded to follow all instructions provided prior to their next appointment.

#### 9.2 Day -3 to -1 (Run-In)

1. Participants will complete the modified WURSS-24 Questionnaires and study diary during the runin period. 9.3

Processing Participants who get COVID-19 or Flu Prior to Day 0

The modified WURSS-24 Questionnaires and daily diaries will be reviewed by clinic staff. As part of the run-in study diary, participants will be asked if between their screening and run-in period if they have had COVID-19 or flu. Clinic staff will identify those participants that self-report they have COVID-19 or flu. Regarding flu, participants will be queried on if they have a diagnosis from their primary care physician (PCP). In the absence of such a diagnosis, based on indicated symptoms, participants will be assessed on a case-by-case basis by the OI.

Both groups of participants will be removed from the study and followed up appropriately.

## 9.4 Day 0 (Baseline)

Eligible participants will be scheduled for the following assessments and will be required to be fasted ( $\geq 8$  hours).

Baseline (Day 0) assessments include:

- 1. Return and review study diaries and modified WURSS-24 Questionnaires
- 2. Review concomitant therapies and current health status
- 3. Assess inclusion and exclusion criteria
- 4. Urine pregnancy test for female potential participants that are of child-bearing potential
- 5. Seated resting BP and HR measurements
- 6. Weight and height measurement
- 7. Randomization of eligible participants
- 8. Collection of blood samples for the analysis of:
  - a. CBC, electrolytes (Na, K, Cl), glucose, eGFR, creatinine, AST, ALT, ALP, and total bilirubin
  - b. ESR, CRP, complement C3, complement C4, IgG, IgM, IgA, CD3+, CD8+, CD4+, CD45+, TCR $\gamma\delta$ +, CD3-CD16+CD56+
  - c. Cytokines, HMGB1, NF-κB, Nrf-2, 8-iso-prostaglandin F2α, CAT, GSH-Px, SOD, MDA, AGEs, HI titers for specific strains of virus for the future analysis
- 9. Administer Vitality Questionnaire (Section 9.9.4)
- 10. Administer COVID-19 OoL (Section 9.9.5)
- 11. Dispense IP and instruct participants on use
- 12. Dispense new study diaries
- 13. Dispense new modified WURSS-24 Questionnaires (Section 9.9.3)
- 14.Record any pre-emergent AEs

The next appointment will be scheduled for Day  $28 \pm 2$  days.

Participants will be reminded to follow all instructions provided prior to their next appointment.

# 9.5 Processing Participants who get COVID-19 or Flu Prior to Day 28 Vaccination

The WURSS-24 Questionnaires and daily diaries will be reviewed by clinic staff. Clinic staff will identify those participants that self-report they have COVID-19 or flu. Regarding flu, participants will be queried on if they have a diagnosis from their PCP. In the absence of such a diagnosis, based on indicated symptoms, participants will be assessed on a case-by-case basis by the QI.

Both group of participants will be removed from the study and followed up appropriately.

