#### **Secondary outcomes:**

The difference between UP360, UP446 and placebo at Day 28 and 56 in:

- 1. Number of confirmed COVID-19 infections
- 2. Number of confirmed flu cases
- 3. Impact of COVID-19 on quality of life assessed by the COVID-19 Impact on QoL Questionnaire
- 4. Over-the-counter cold and flu medication use

The difference between UP360, UP446 and placebo at Day 56 in:

- 1. Number of hospitalizations due to COVID-19
- 2. Number of hospitalizations due to flu

The difference in change between UP360, UP446 and placebo from baseline at Day 28 and 56 in:

- 1. Erythrocyte sedimentation rate (ESR) and C-reactive protein (CRP)
- 2. Hematology parameters: white blood cell (WBC) count with differential (neutrophils, lymphocytes, monocytes, eosinophils, basophils), reticulocyte count, red blood cell (RBC) count, hemoglobin, hematocrit, platelet count, RBC indices (mean corpuscular volume (MCV), mean corpuscular hemoglobin (MCH), mean corpuscular hemoglobin concentration (MCHC), and red cell distribution width (RDW)
- 3. Complement C3 and C4 proteins
- 4. Mean global severity index, as measured by area under the curve (AUC) for the Modified Wisconsin Upper Respiratory Symptom Survey (WURSS)-24 daily symptom scores
- 5. Mean symptom severity scores, as measured by AUC for the WURSS-24 daily severity symptom scores
- 6. Number of well days (defined as days scored as 0 (not sick) for the question, "How sick do you feel today?") as assessed by the Modified WURSS-24 Questionnaire
- 7. Number of sick days (defined as days scored as any number from 1 through 7 (sick) for the question, "How sick do you feel today?") as assessed by the Modified WURSS-24 Questionnaire
- 8. Frequency of common upper respiratory tract infection (UTRI) symptoms as assessed by the Modified WURSS-24 Questionnaire
- 9. Duration of common UTRI symptoms as assessed by the Modified WURSS-24 Questionnaire
- 10. Severity of common UTRI symptoms as assessed by the Modified WURSS-24 Questionnaire
- 11. Vitality and quality of life as assessed by the Vitality and Quality of Life (QoL) Questionnaire

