# 7.2 Exclusion Criteria

- 1. Women who are pregnant, breast feeding, or planning to become pregnant during the study
- 2. Participant has a known allergy to the active or inactive ingredients in UP360, UP446, placebo, or QIV
- 3. Unvaccinated participants with flu prior to baseline from September 2020 or prior to Day 28 vaccination
- 4. Participants self-reporting a diagnosis of COVID-19 prior to baseline or prior to Day 28 vaccination
- 5. Participants who have received the COVID-19 vaccine
- 6. Current use of prescribed immunomodulators (including corticosteroids) such as immunosuppressants or immunostimulants within 4 weeks of baseline (see Section 7.3)
- 7. Current use of dietary supplement or herbal medicines associated with boosting or modulating the immune system unless willing to washout (see Section 7.3.2)

- 8. Participation in other clinical research studies 30 days prior to enrollment will be assessed on a caseby-case basis by the QI
- 9. Individuals who are unable to give informed consent
- 10. Any other condition, chronic disease, or lifestyle factor, that, in the opinion of the QI, may adversely affect the participant's ability to complete the study or its measures or pose significant risk to the participant

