#### Assessments include:

- 1. Return and review study diaries and modified WURSS-24 Questionnaires
- 2. Return unused investigational product in the original packaging and remnants and calculate compliance by counting the returned unused investigational product
- 3. Review concomitant therapies and adverse events
- 4. Seated BP and HR measurements
- 5. Collection of blood samples for the analysis of:
  - a. CBC, electrolytes (Na, K, Cl), glucose, eGFR, creatinine, AST, ALT, ALP, and total bilirubin
  - b. ESR, CRP, complement C3, complement C4, IgG, IgM, IgA, CD3+, CD8+, CD4+, CD45+, TCR $\gamma\delta$ +, CD3-CD16+CD56+
  - c. Cytokines, HMGB1, NF-κB, Nrf-2, 8-iso-prostaglandin F2α, CAT, GSH-Px, SOD, MDA, AGEs, HI titers for specific strains of virus for future analysis
- 6. Administer Vitality Questionnaire (Section 9.9.4)
- 7. Administer COVID-19 QoL (Section 9.9.5)
- 8. Administer flu vaccine (QIV)
- 9. Dispense new IP
- 10. Dispense new study diaries
- 11. Dispense new modified WURSS-24 Questionnaires (Section 9.9.3)

The next appointment will be scheduled for Day  $56 \pm 2$  days.

Participants will be reminded to follow all instructions provided prior to their next appointment.

## 9.7 Processing Participants who get COVID-19 or Flu After Vaccination and Prior to Day 56

The WURSS-24 Questionnaires and daily diaries will be reviewed by clinic staff. Clinic staff will identify those participants that self-report they have COVID-19 or flu. Regarding flu, participants will be queried on if they have a diagnosis from their PCP. In the absence of such a diagnosis, based on indicated symptoms, participants will be assessed on a case-by-case basis by the QI.

Participants with self-reported diagnosis COVID-19 will be removed from the study. A COVID-19 diagnosis will be considered an AE and AE follow-up procedures will be followed.

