### 10.2.2 Treatment and Follow-up of Laboratory Abnormalities

In the event of participant-initiated withdrawal or clinically significant unexplained abnormal laboratory test values, the participant will be withdrawn from the investigational product or placebo and will remain in the study and be required to attend all remaining study visits as part of a safety arm.

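### Randomized participants are removed for reporting COVID-19 (or flu before Day 28), yet these infections, their hospitalizations and WURSS-24 symptoms to Day 56 are between-arm outcomes with no stated collection after removal

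*Protocol*

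**What the plan says.** **Order of events.** Protocol Section 8.10 states: "Enrolled participants will be randomized to the different study arms at day 0". Dosing also starts on Day 0 (Section 8.6).

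**Removal rules that act after that.**
- Section 9.5, for self-reported COVID-19 or flu between Day 0 and the Day 28 vaccination: "Both group of participants will be removed from the study and followed up appropriately".
- Section 9.7, between Day 28 and Day 56: "Participants with self-reported diagnosis COVID-19 will be removed from the study". The diagnosis is handled as an adverse event. No removal is stated for flu in this window.
- Section 7.2, exclusion criterion 4: "Participants self-reporting a diagnosis of COVID-19 prior to baseline or prior to Day 28 vaccination". Criterion 3 does the same for flu. Both make an event after randomization a ground of ineligibility.

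**Outcomes.** Section 5 lists as between-arm secondary outcomes at Day 28 and 56 "Number of confirmed COVID-19 infections" and "Number of confirmed flu cases", and at Day 56 "Number of hospitalizations due to COVID-19" and the same for flu. It also lists WURSS-24 AUC, well and sick days, and symptom frequency, duration and severity at Day 28 and 56. The primary immune markers are measured on the same two days.

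**Analysis sets and missing data.** ITT (Section 11.2) requires dosing and some effectiveness data after randomization. The per-protocol set requires every visit and procedure connected with the primary variables. Section 11.3 provides LOCF or multiple imputation as a sensitivity analysis for ITT.

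**The concern.** The rule takes people out of the trial for having an event that the trial sets out to compare. The products are tested for immune support, so the chance of infection may depend on the arm. If it does, the chance of being removed depends on the arm too, and what goes unrecorded is the course of illness in the people who became ill. Randomization does not protect a comparison against that kind of loss, and imputation from healthy participants cannot recover an illness that was not observed. The secondary outcomes on infection, hospitalization and symptoms are the most exposed. The Day 28 and Day 56 immune markers are touched as well.

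**Working it through.** **1. What survives for a removed participant.** The outcomes in Section 5, set against the routes the protocol offers:

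| Outcome | Route by which data may survive | What is not provided for |
|---|---|---|
| Triggering infection | Known to staff, since it prompts the removal | Whether it enters the Day 28 and 56 totals; before Day 28, criteria 3 and 4 make the person ineligible |
| Later hospitalization | After Day 28, adverse event follow-up (9.7, 10.2.1); hospitalization is a serious adverse event (10.1.2, 10.3) | Counting it as an outcome; before Day 28 the type and length of follow-up are not specified |
| WURSS-24 course | Diaries and questionnaires completed up to removal | The rest of the illness. Section 10.1.1 says WURSS-24 symptoms are not classified as adverse events, so safety follow-up does not replace it |
| Day 28 and 56 blood samples | One end-of-study evaluation at withdrawal, if possible (7.5) | Samples at the scheduled days |

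**2. Analysis sets.** A participant removed before completing the primary visits leaves the per-protocol set. In ITT, the person stays if a returned diary or questionnaire counts as effectiveness data, and later values are then missing or imputed. If removal is before Day 28 and no withdrawal sample exists, the last marker value is baseline, so LOCF sets the change to 0. With k such participants of 25, and the mean change of the others unaltered, the arm's mean change is multiplied by (25 − k)/25: 0.96, 0.92 and 0.88 for k = 1, 2 and 3.

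**3. The plan's own figure.** Section 11.1 gives 25 per arm with 20% loss to follow-up. 20/(1 − 0.20) = 25, so the plan is consistent with 20 evaluable per arm. The effect-size step cannot be checked because no standard deviations are given.

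**4. How many are affected.** The protocol states no infection rate, so the 56-day removal risk r is an assumption. Expected removals are 75r, and the chance of at least one is 1 − (1 − r)^75. If removals come on top of the planned 20% loss, evaluable n per arm is 20(1 − r).

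| Assumed r | Expected removals of 75 | Chance of at least one | Evaluable per arm |
|---|---|---|---|
| 2% | 1.5 | 0.78 | 19.6 |
| 5% | 3.75 | 0.98 | 19.0 |
| 10% | 7.5 | over 0.99 | 18.0 |

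**5. Power.** The standardized difference with 80% power at 20 per arm is d = (z_α + z_0.80) × √(2/20), where z_α is the critical value of the test. This gives 0.786 (one-sided 0.05), 0.886 (two-sided 0.05) and 1.023 (two-sided 0.05/3). A three-arm F test gives 1.008. Holding each d fixed, power is about 0.78 at 19 per arm and 0.75 to 0.76 at 18.

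**6. Scale of the bias in symptom days.** If k of 25 in an arm each have s sick days unrecorded, the arm's mean per randomized participant is understated by k × s/25. With an assumed k = 3 in one arm, 0 in another, and s = 7, that is 3 × 7/25 = 0.84 days. This is an upper bound for that scenario, because sick days before removal may already be in a returned diary.

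**The case against.** There is a fair case for the rule. In a vaccine-challenge study, an infection can itself disturb the immune markers, so taking infected participants out of the marker comparison is defensible. That justifies a rule for the marker analysis. It does not justify ending the collection of infection, hospitalization and symptom outcomes. It also limits what the fix can gain: if post-infection samples are left out of the primary analysis, those data are lost to that analysis either way.

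A reader might infer several stronger points that the documents do not support:

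- **All data stop at the first report.** Section 7.5 offers an evaluation at withdrawal if possible. Cases are identified from WURSS-24 questionnaires and diaries, whose return is scheduled at the Day 28 and Day 56 visits. A case found at Day 56 may lose little.
- **Hospitalizations are near zero by construction.** The adverse event and serious adverse event routes can record them, and flu after Day 28 carries no removal. They are not reliably captured as outcomes, which is a weaker statement.
- **ITT drops these people.** Its definition does not do so automatically, and Section 11.3 allows imputation.
- **Section 10.2.2 contradicts the rule.** That section says that some participants taken off product "will remain in the study and be required to attend all remaining study visits", but its triggers are participant-initiated withdrawal and unexplained laboratory abnormalities. It shows that follow-up off product is feasible here; it does not govern infections.
- **The immune markers are biased in a known direction.** Nothing in the protocol says which way infection would shift them.

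**Conclusion.** The point holds in a bounded form. Sections 9.5 and 9.7 and exclusion criteria 3 and 4 conflict with the secondary outcomes in Section 5, and no section provides for collecting those outcomes to Day 56 in the people removed. Following the plan as written gives missing data that depend on the outcome and may differ by arm.

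The conflict rests on the text alone. Its size does not: the infection risk, any imbalance between arms and the number of sick days lost are all assumptions. Over the assumed 2% to 10% risk the effect on power is minor even if removals come on top of the 20% allowance. The harm is possible bias in the infection, hospitalization and symptom comparisons, with a smaller effect on the markers through missing or carried-forward values. With few events expected, one or two unrecorded illnesses can alter a comparison of 25 per arm.

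**What to change.** Reconcile Section 5, exclusion criteria 3 and 4, Sections 9.5 and 9.7, and the analysis sets in Section 11.2. Specifically:

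- In 9.5 and 9.7, replace removal from the study with continued outcome collection to Day 56: diary and WURSS-24, infection status and hospitalization status, by phone if a visit is not possible.
- State that the triggering infection and any hospitalization count as outcomes, and use all randomized participants as denominators.
- For the immune markers, treat infection as an intercurrent event. State whether post-infection samples are used in the primary analysis, and make the alternative a sensitivity analysis.

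Whether such participants continue product or are vaccinated is for the sponsor and investigator. How criteria 3 and 4 bear on vaccination should be reconciled by them, and no rule is proposed here.

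The cost is amendment wording and a few phone contacts. The small downside is that some later data will come from people who are ill or off product. Data that are not collected during the trial cannot be recovered at analysis.
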